**Effect of in vitro fertilisation (IVF) hormonal
therapy on metabolic, endocrine and
inflammatory status in IVF-conceived
pregnancy**

NCT03426228

Chapter 1: Aim of the study and Objectives

1. To explore the short-term effects of IVF hormonal therapy on maternal metabolic and inflammatory status, including:
 - i. Risk of glucose intolerance and insulin resistance
 - ii. Risk of other metabolic, endocrine and inflammatory disturbances (including lipid profile, gut microflora and thyroid function)
2. To identify possible early predictors of GDM and other metabolic-related adverse outcomes in IVF-conceived pregnancies.

Chapter 2: General Methods

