2.2. Study Design

The presented study is a longitudinal quantitative cohort study (non-experimental), whereby blood samples were collected at different stages during IVF therapy.

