2.4. Study Population

- **Pregnant group:** received IVF therapy and tested positive for pregnancy at 4 weeks, and continued taking IVF hormonal therapy until 12 weeks of pregnancy.
- **Non-pregnant:** received IVF therapy and tested negative for pregnancy at 4 weeks, and stopped taking IVF hormonal therapy at that point.

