**Effect of in vitro fertilisation (IVF) hormonal therapy
on metabolic, endocrine and inflammatory status in
IVF-conceived pregnancy**

NCT03426228

Statistical Analysis

1. Effects of IVF Therapy

Data analysis was performed with the Statistical Package for the Social Sciences (SPSS) software version 21.0 for Windows (SPSS, Chicago, IL). Parameters normality was confirmed with the Shapiro-Wilk test. Non-parametric Wilcoxon test for two related samples was conducted to assess changes at baseline vs. post-IVF treatment (12 weeks) within groups (pregnant or non-pregnant). Non-parametric Mann-Whitney U test for two independent samples was used to compare the two groups pregnant vs. non-pregnant, at baseline and at 12 weeks. Bivariate correlation was used to determine correlations between the different anthropometric and metabolic parameters at week 12. Data from the two groups were analysed separately. Linear regression was used for assessment of association of change in glucose level at 12 weeks (dependent variable) with change in other anthropometric and biochemical parameters, separately for each group. Changes in glucose and insulin levels (and the resulting HOMA-IR) throughout IVF therapy (baseline, 2, 4 and 12 weeks) were determined with the mixed model for repeated measures test. Significance level was set at $p < 0.05$ and 95% confidence interval.

2. Anthropometrics and Biomarkers of Gestational Diabetes Mellitus (GDM)

In the pregnant group, the Mann-Whitney U test for two independent samples was used to compare data at baseline with 12 weeks, for comparison between women who later developed GDM to the non-GDM group. Changes at baseline, 4 and at 12 weeks were assessed by non-parametric Wilcoxon test (two related samples) within groups (future GDM or non-future GDM women). Predictors of GDM were assessed using binary logistic regression, adjusting for the following variables: age and history of PCOS.

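### For six markers, pregnant and non-pregnant women are compared only on unadjusted levels; no between-group comparison of change or baseline-adjusted comparison is planned

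*SAP*

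**What the plan says.** SAP section 1 (Effects of IVF Therapy) assesses change from baseline to week 12 with a Wilcoxon test run separately in the pregnant and the non-pregnant women. The Mann-Whitney test is then "used to compare the two groups pregnant vs. non-pregnant, at baseline and at 12 weeks". A linear regression relates change in glucose to "change in other anthropometric and biochemical parameters, separately for each group". For glucose, insulin and HOMA-IR only, changes over the four visits "were determined with the mixed model for repeated measures test"; the terms of that model are not listed. The SAP's only covariate adjustment is in section 2, in the logistic regression for GDM, "adjusting for the following variables: age and history of PCOS".

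Protocol Table 1 schedules HbA1c, TSH, lipid profile, adiponectin, LBP and body weight at baseline and at week 12. Appendix 2 agrees for the blood markers. Protocol section 2.2 describes a non-experimental cohort. Under section 2.4 the groups are defined by the week-4 test: the pregnant group "tested positive for pregnancy at 4 weeks, and continued taking IVF hormonal therapy until 12 weeks of pregnancy", while the non-pregnant group stopped therapy at week 4. Objective 1 is "To explore the short-term effects of IVF hormonal therapy on maternal metabolic and inflammatory status"; it does not name the pregnant versus non-pregnant contrast.

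**The concern.** Nothing in the design balances the two groups before therapy. Women who conceive may already differ from those who do not in weight, lipids or adiponectin. A difference in week-12 levels then mixes what was there at baseline with what changed afterwards, and the planned test cannot separate the two. The error can run either way: a carried-over gap can look like a group effect, and an opposite gap can hide a real difference in change.

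The within-group Wilcoxon tests do not fill the hole. A significant change in one group and a non-significant change in the other is not a test of whether the groups changed differently. For these six markers (counting the lipid profile as one), the plan therefore contains no result that answers that question, although the paired values needed for it are scheduled.

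**Working it through.** **Step 1. Text check.** Each analysis in SAP section 1, set against the six markers:

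| Analysis | Covers the six markers | Contrasts the groups | Uses change or baseline value |
|---|---|---|---|
| Wilcoxon, baseline v week 12 | yes | no | change, within group |
| Mann-Whitney, baseline and week 12 | yes | yes | no, levels only |
| Correlations at week 12 | yes | no, groups separate | no |
| Regression for change in glucose | only as explanatory variables | no, one fit per group | change |
| Mixed model | no (glucose, insulin, HOMA-IR) | not stated | all four visits |

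Only the Mann-Whitney row contrasts the groups on these markers, and it uses neither change nor the baseline value.

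**Step 2. Inputs.** The documents state no sample size, SD, correlation or baseline gap, so there is no figure of theirs to reproduce. Everything below is illustration. Assumed: gap 0.2 or 0.3 SD; n = 40 or 80 per group; baseline to week-12 correlation ρ = 0.3, 0.6 or 0.8; normal data with SD 1; equal true effect in both groups. Significance is 0.05 as in the SAP, taken as two-sided.

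**Step 3. Week-12 test when the gap persists in full.** Normal approximation: shift = gap × √(0.955 × n/2), and rejection probability = P(|Z + shift| > 1.96).
- n = 40: √19.1 = 4.370. Gap 0.2: shift 0.874, 14.1%. Gap 0.3: shift 1.311, 25.9%.
- n = 80: √38.2 = 6.181. Gap 0.2: shift 1.236, 23.5%. Gap 0.3: shift 1.854, 45.8%.

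**Step 4. Can the baseline test be relied on?** It faces the same gap with the same n, so it misses the gap with the complementary probability: 85.9% and 74.1% at n = 40; 76.5% and 54.2% at n = 80.

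**Step 5. Simulation** (20,000 runs per cell). Per cent of studies with p < 0.05, at ρ = 0.3 / 0.6 / 0.8.

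(a) Gap persists in full:

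| Gap, n per group | Week-12 Mann-Whitney | Change-score Mann-Whitney | Baseline-adjusted regression |
|---|---|---|---|
| 0.2, 40 | 13.5 / 13.9 / 13.8 | 4.6 to 5.3 | 9.6 / 7.3 / 5.8 |
| 0.3, 40 | 25.5 / 24.6 / 25.2 | 4.6 to 5.3 | 16.7 / 10.0 / 7.0 |
| 0.2, 80 | 23.0 / 23.2 / 22.7 | 4.6 to 5.3 | 14.8 / 9.4 / 7.0 |
| 0.3, 80 | 45.1 / 45.1 / 45.1 | 4.6 to 5.3 | 27.6 / 15.4 / 9.7 |

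(b) Gap regresses to the mean (week-12 gap = ρ × baseline gap):

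| Gap, n per group | Week-12 Mann-Whitney | Change-score Mann-Whitney | Baseline-adjusted regression |
|---|---|---|---|
| 0.2, 40 | 5.3 / 8.0 / 10.2 | 7.8 / 6.7 / 5.6 | 4.7 to 5.2 |
| 0.3, 40 | 6.6 / 12.0 / 17.3 | 11.6 / 8.7 / 6.8 | 4.7 to 5.2 |
| 0.2, 80 | 6.6 / 11.2 / 17.0 | 11.3 / 8.9 / 6.6 | 4.7 to 5.2 |
| 0.3, 80 | 8.2 / 19.5 / 31.5 | 19.1 / 12.9 / 8.8 | 4.7 to 5.2 |

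With no gap, all three tests reject in 4.6 to 5.2%. Among the significant week-12 results in (a), the baseline test was not significant in 34 to 60% at ρ = 0.6, and in 23 to 75% over all three correlations.

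**Step 6. Where change scores do worse.** Under (b) the standardised shift is ρ × gap for the week-12 test and gap × √((1−ρ)/2) for change. Setting them equal gives 2ρ² + ρ − 1 = 0, so ρ = 0.5. Below that, change scores reject more often than the week-12 test.

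**Step 7. Masking.** Take a baseline gap of −0.4 SD and a true difference in change of +0.4 SD, with 30 to 100 per group, ρ 0.5 to 0.9 and 2,000 runs per setting. The week-12 test is significant in about 4 to 6% of studies; a comparison of change finds the difference in about 32 to 100%.

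**Step 8. Side-by-side Wilcoxon tests.** With equal true change and within-group power p, exactly one of the two is significant with probability 2p(1−p): 42%, 50% and 32% at p = 0.3, 0.5 and 0.8.

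**The case against.** The strongest reply is that the week-12 test is not invalid. If a gap persists, the groups really do differ at week 12, and a test of levels that says so is right. It misleads only a reader who takes the difference as having arisen after baseline, and the documents do not draw that inference. Objective 1 is exploratory and does not name this contrast; the within-group Wilcoxon, which uses each woman's own baseline, serves it more directly. The plan also tests the groups at baseline, so a reader would see both results, and larger gaps would be detected more often than those assumed here. No passage reports an imbalance.

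Much of this stands. The harm is conditional, and the inputs are assumptions. But the SAP itself plans the between-group tests under a heading about effects of therapy, and a comparison of levels alone cannot show a difference in effect. The baseline test can reveal a gap but not remove it, and a non-significant result is weak reassurance at the sizes shown.

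It is also true that neither alternative is always right. Baseline adjustment reaches 28% when the gap persists, and change scores reach 19% under regression to the mean, where the planned test gives 8%. That is a reason to state the assumption and show both results, not to leave the baseline value unused. Finally, a better contrast still does not separate pregnancy from continued hormone therapy.

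**Conclusion.** The concern holds. The omission is plain from the text: for HbA1c, TSH, lipids, adiponectin, LBP and weight, the only pregnant versus non-pregnant comparison is of unadjusted levels.

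Its size depends on assumptions the documents cannot settle. For gaps of 0.2 to 0.3 SD, the week-12 test would be significant without any differential effect in about 14 to 26% (40 per group) or 24 to 46% (80 per group) of studies if the gap persists. If the gap regresses to the mean, the figures are about 5 to 17% and 7 to 32%. Baseline adjustment rejected less often than the week-12 test in every cell; change scores did so except under regression to the mean at correlation 0.3. No baseline gap and no wrong result has been shown. This should be fixed because the remedy is cheap and these are the only between-group results for the six markers.

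For glucose, insulin and HOMA-IR the point is one of clarification only: the mixed model may already include group by time.

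**What to change.** 1. For each of the six markers, analyse both groups together. Report with a 95% CI either the between-group difference in change (week 12 minus baseline) or the week-12 difference adjusted for the baseline value, on the log scale if skewed.
2. Name one as the main result and give the other as a sensitivity analysis, with the reason. Change scores assume that a baseline gap would persist in full; baseline adjustment assumes that it regresses to the mean. If the two disagree, say that the conclusion depends on that assumption.
3. If further covariates are used, age and history of PCOS are natural candidates because SAP section 2 already uses them; their relevance to this contrast should be argued.
4. List the mixed-model terms for glucose, insulin and HOMA-IR, and report the week-12 group by time contrast if it is not already there.
5. Keep the level-only Mann-Whitney and within-group Wilcoxon tests as descriptive.
6. State that the contrast mixes pregnancy with continued therapy. Protocol section 2.4 has therapy running until 12 weeks of pregnancy, while section 2.6 places the week-12 sample one week after therapy ends. These need to be reconciled, or the different week counts explained.

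**Cost.** SAP wording and a reanalysis. The SAP is written in the past tense and its regression already uses changes in these parameters, so no new samples should be needed. There will be two results per marker, and some significant week-12 differences may disappear. Relative to the week-12 comparison, the variance is 2(1−ρ) for change and 1−ρ² for baseline adjustment: 1.40 and 0.91 at ρ = 0.3, 1.00 and 0.75 at 0.5, 0.40 and 0.36 at 0.8. Change scores therefore lose precision below ρ = 0.5; baseline adjustment does not, but it needs a regression model.

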2.7. Blood Tests

A trained nurse was in charge of measuring anthropometrics and clinical parameters (e.g. weight and blood pressure), in addition to taking fasting blood samples. The socio-demographics, medical and pregnancy histories of each patient

were recorded in their file. Blood tests were conducted at in the phlebotomy room and transferred to the lab (in-house) for analysis. Tests results were available on the clinics internal server at the end of each day.

Table 1: List of Blood Tests at Each Stage of the Study

Type of Tests	Phase 1- Baseline (Start IVF treatment)	Phase 2- Week 2 (Egg retrieval)	Phase 3- Week 4 (β - HCG test)	Phase 4- Week 12 (Final)
Female reproductive hormones: FSH, LH, oestrogen, progesterone	✓	✓	✓	
HbA1c	✓			✓
Fasting glucose	✓	✓	✓	✓
Fasting insulin	✓	✓	✓	✓
TSH	✓			✓
Fasting lipid profile	✓			✓
Adiponectin	✓			✓
LBP	✓			✓
β -HCG pregnancy	✓		✓	
Body weight	✓			✓

*Green highlight represents stage where non-pregnant vs. pregnant women groups were distinguished; FSH: follicle-stimulating hormones; LH: luteinizing hormone; HbA1c: glycated haemoglobin A1c; TSH: thyroid-stimulating hormone; LBP: lipopolysaccharide binding protein; β -HCG: beta-human chorionic gonadotrophin

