Appendix 2. Participants Study Tests

Effects of fertility drugs on glucose homeostasis, and other metabolic parameters on patients undergoing In Vitro Fertilisation (IVF) [NCT03426228](#)

IVF MEDICATION & METABOLIC PARAMETERS				
Baseline	Week2	Week 2	Week 4	Week 12
Start IVF Therapy	Pre-OPU	Embryo Transfer	+/- β -HCG	Final
A1C Fasting glucose Serum insulin Lipid profile Hormonal Profile (AMH, LH, FSH, progesterone, oestrogen) TSH LBP Adiponectin	Fasting glucose Serum insulin Hormonal profile (LH, progesterone, oestrogen)	Hormonal Profile (progesterone, oestrogen)	Fasting glucose Serum insulin Hormonal profile (progesterone, oestrogen, β -HCG)	HbA1c Fasting glucose Serum insulin Lipid profile TSH LBP Adiponectin

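### Could the open parameter list in the glucose regression let HOMA-IR, itself computed from glucose, produce an association by arithmetic alone?

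*SAP*

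**What the plan says.** SAP section 1 (Effects of IVF Therapy) has three sentences that bear on this.

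- **Correlations:** "Bivariate correlation was used to determine correlations between the different anthropometric and metabolic parameters at week 12".
- **Regression:** the "association of change in glucose level at 12 weeks (dependent variable) with change in other anthropometric and biochemical parameters", fitted separately in each group.
- **Repeated measures:** "Changes in glucose and insulin levels (and the resulting HOMA-IR) throughout IVF therapy (baseline, 2, 4 and 12 weeks") are examined with a mixed model. This is the only place where either document names HOMA-IR.

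The first two give no list of variables and exclude none. The threshold is given as "Significance level was set at $p < 0.05$ and 95% confidence interval".

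In the protocol, the first objective in Chapter 1 includes "Risk of glucose intolerance and insulin resistance". Section 2.7, Table 1 schedules fasting glucose and fasting insulin at all four phases. The week-12 column of Appendix 2 reads "HbA1c Fasting glucose Serum insulin Lipid profile TSH LBP Adiponectin". HOMA-IR is in neither table, nor in the blood-analysis list of Appendix 1.

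**The concern.** HOMA-IR is the only index of insulin resistance that the documents name, and insulin resistance belongs to the first aim. The SAP's wording is loose enough to admit HOMA-IR both as a predictor of change in glucose and as a week-12 correlate. Because HOMA-IR is built from glucose and insulin, change in HOMA-IR contains change in glucose. A regression of one on the other can be significant when glucose and insulin are unrelated. At week 12, HOMA-IR would correlate with both of its components by construction.

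At stake is a misleading statement that insulin resistance drives the rise in glucose. No primary test or sample size would be affected.

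A related worry is that the change-score regression leaves out baseline glucose, which might distort the association with other markers.

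**Working it through.** The plan gives no figure to reproduce: it states no group size, standard deviation or correlation. All inputs below are assumptions, apart from the 0.05 level (SAP section 1, taken as two-sided).

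**Assumed inputs.** HOMA-IR = glucose × insulin / 22.5 (the constant does not affect correlations). Glucose and insulin are log-normal and independent. The correlation between visits is 0.5. Glucose CV is 6–15%, insulin CV 30–70%, and n is 30, 50 or 100 per group.

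**Week-12 correlations, exact.** For independent glucose (G) and insulin (I) with coefficients of variation c_G and c_I, let D = √(c_G² + c_I² + c_G²c_I²). Then r(G, HOMA-IR) = c_G/D and r(I, HOMA-IR) = c_I/D.

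For c_G = 0.10 and c_I = 0.50, D = √(0.0100 + 0.2500 + 0.0025) = 0.512. So r(G, HOMA-IR) = 0.10/0.512 = 0.195 and r(I, HOMA-IR) = 0.50/0.512 = 0.98.

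**Change scores, simulated.** In the same setting r(change in G, change in HOMA-IR) = 0.19, against 0.00 for change in insulin. As a check by Fisher's z at n = 50: atanh(0.19) × √47 = 0.192 × 6.86 = 1.32, and P(Z > 1.96 − 1.32) = 0.26. The simulation gave 0.25.

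**Share of studies with p<0.05 for change in glucose when nothing is related (3,000 runs per cell):**

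| CV glucose, insulin | HOMA-IR, n=30 | n=50 | n=100 | Insulin, all n |
|---|---|---|---|---|
| 6%, 70% | 0.08 | 0.09 | 0.14 | 0.051–0.057 |
| 8%, 50% | 0.14 | 0.18 | 0.33 | 0.049–0.052 |
| 10%, 50% | 0.18 | 0.25 | 0.47 | 0.045–0.050 |
| 10%, 30% | 0.40 | 0.62 | 0.89 | 0.048–0.053 |
| 15%, 30% | 0.72 | 0.90 | 1.00 | 0.044–0.050 |

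If changes in insulin and HOMA-IR entered one model together, R² would be 0.57–0.88 and the overall test would reject in about 100% of runs. The SAP specifies no such model. It does not even say that the regression is multivariable.

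**Does the plan lead there?** Set the three sentences side by side. Where the authors wanted HOMA-IR they named it, as a response followed over time, and there it does no harm. The regression asks for parameters other than glucose. The protocol's lists of what is collected hold laboratory tests, body measurements and history, with no derived resistance index. Measured tests are therefore the natural reading of the regression sentence. The word used for the correlations, metabolic, is broader and could take HOMA-IR in.

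**Baseline glucose.** Let a marker's change correlate b with baseline glucose and w with week-12 glucose, with visit correlation 0.5 and equal variances. Its correlation with raw change in glucose is (w − b)/√(2 − 2 × 0.5) = w − b. Its partial correlation with week-12 glucose given baseline is (w − 0.5b)/√((1 − b²) × 0.75).

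- b = −0.3, w = 0: raw 0.30, adjusted 0.18.
- b = −0.3, w = −0.15: raw 0.15, adjusted 0.
- b = −0.3, w = −0.3: raw 0, adjusted −0.18.

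The two models answer different questions, and which one shows an association depends on a correlation pattern that the documents do not give.

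**The case for a change.** The best case for a change is that a plan should close off a known artefact before results are seen. Insulin resistance is a stated aim, HOMA-IR is computable at baseline and week 12, and an analyst could enter it in both analyses without departing from the text. One line would prevent this and no new data are needed. The direction of the artefact does not depend on the assumed inputs.

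Much of that stands. The lists are open, the coupling is genuine, and any reported HOMA-IR–glucose or HOMA-IR–insulin correlation should be read as largely arithmetic.

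What does not stand is the step from a possible misuse to a fault in the plan. Nothing in the documents shows that HOMA-IR was entered or was meant to be. The same sentence that names it says it results from glucose and insulin, so the coupling is in plain view. Labelling coupled cells in a correlation table helps a reader but alters no result. A baseline-adjusted model beside the raw-change model would be a preference between two estimands, and the data could not settle a disagreement between them.

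**Conclusion.** No change to the plan follows. SAP section 1 leaves the variables of an exploratory regression and a correlation table unlisted, and analysts can fill that gap sensibly from the protocol's own test lists. Fasting insulin is measured at every phase and, as a predictor of change in glucose, keeps the false-positive rate at 4.4–5.7% in every setting tried.

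Only if change in HOMA-IR were entered instead would the rate rise, to between 8% and almost 100% depending on the spread of glucose and insulin and on group size. That range assumes the product form of HOMA-IR, independent glucose and insulin, and CVs, visit correlation and group sizes that the documents do not supply. It describes a model the plan does not state. Omitting baseline glucose is a fair trade-off, since neither version of the model is better without knowing how each marker relates to glucose at the two visits.

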2.6. Study Protocol

After an overnight fast of 8 hours, there was collection of 10 ml of blood at four pre-defined time points during the IVF protocol:

1. **Phase 1** – At baseline, egg maturation (starting IVF therapy)
2. **Phase 2** – Week 2 – Egg retrieval (OPU procedure)
3. **Phase 3** – Week 4 – At pregnancy test (β -HCG test)
4. **Phase 4** – Week 12 (one week after completing IVF hormonal therapy for pregnant group).

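### Does leaving the covariance structure of the four-visit mixed model unnamed put the glucose and insulin results at risk?

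*SAP*

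**What the plan says.** SAP section 1 describes the model in one clause: changes in glucose, insulin and HOMA-IR "throughout IVF therapy (baseline, 2, 4 and 12 weeks) were determined with the mixed model for repeated measures test". It gives no covariance structure, degrees-of-freedom method, contrasts or analysis scale, and nothing in the protocol adds them. Protocol 2.6 and Table 1 confirm four samples of glucose and insulin, at baseline and weeks 2, 4 and 12.

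The same SAP section plans a second analysis of the longest interval: "Non-parametric Wilcoxon test for two related samples was conducted to assess changes at baseline vs. post-IVF treatment (12 weeks) within groups". SAP section 2 adds Wilcoxon tests on baseline, week 4 and week 12, within the pregnant women who did and did not later develop GDM.

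Two neighbouring sentences are equally brief. One is on distributional checks ("Parameters normality was confirmed with the Shapiro-Wilk test"). The other is on regression ("Linear regression was used for assessment of association of change in glucose level at 12 weeks (dependent variable"), with no mention of residuals.

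**The concern.** Equal correlation between every pair of visits is hard to take for granted here. The gaps are 2, 2 and 8 weeks, and treatment changes along the way: non-pregnant women "tested negative for pregnancy at 4 weeks, and stopped taking IVF hormonal therapy at that point", while pregnant women continue. Several covariance structures fit the SAP's sentence, and they give different standard errors for the same data. If correlation fades with time and equal correlation is assumed, long-interval changes look too precise and short-interval changes too imprecise.

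The model also carries weight. The first aim is "To explore the short-term effects of IVF hormonal therapy on maternal metabolic and inflammatory status". Within SAP section 1 only the mixed model uses the week-2 and week-4 samples, and week 2 has no other named test anywhere in the SAP. Setting the lowest and highest simulated week-12 error rates side by side gives a spread from 0.3% to 9%, which looks alarming beside a nominal 5%.

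**Working it through.** **Inputs.** From the documents: visits at weeks 0, 2, 4 and 12, and a significance level of 0.05 (taken as two-sided). The plan gives no error rate, power, sample size, standard deviation or correlation, so it has no figure to reproduce. Assumed: complete data, equal variances, and three correlation patterns:

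- constant: 0.6 for every pair;
- mild decline: 0.75 × (2/3)^(t/12) at a gap of t weeks;
- stronger decline: 0.75 × 0.4^(t/12).

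**Formula (large sample).** Let ρ be the true correlation between the two visits compared, and ρ̄ the mean of the six pairwise correlations. The true variance of the difference is proportional to 1 − ρ. An equal-correlation model estimates it as 1 − ρ̄, an independent-visits model as 1, and an unstructured model as 1 − ρ. With k the ratio of estimated to true variance, the false-positive rate is 2 × [1 − Φ(1.96 × √k)].

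**Correlations**

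| Pair of weeks | 0–2 | 0–4 | 0–12 | 2–4 | 2–12 | 4–12 | Mean ρ̄ |
|---|---|---|---|---|---|---|---|
| Mild | 0.701 | 0.655 | 0.500 | 0.701 | 0.535 | 0.572 | 0.611 |
| Stronger | 0.644 | 0.553 | 0.300 | 0.644 | 0.350 | 0.407 | 0.483 |

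**Equal-correlation model**

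- Week 12 v baseline, mild: k = 0.389/0.500 = 0.778; 1.96√k = 1.729; rate 8.4%.
- Week 12 v baseline, stronger: k = 0.517/0.700 = 0.739; 1.96√k = 1.685; rate 9.2%.
- Week 2 v baseline, mild: k = 0.389/0.299 = 1.302; 1.96√k = 2.236; rate 2.5%.
- Week 2 v baseline, stronger: k = 0.517/0.356 = 1.452; 1.96√k = 2.362; rate 1.8%.
- Constant correlation: k = 1; rate 5.0% for every contrast.

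**Independent visits**, week 12 v baseline, constant 0.6: k = 1/0.4 = 2.5; 1.96√k = 3.099; rate 0.2%.

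**Unstructured**: k = 1 throughout; rate 5.0%.

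**Simulation** (n = 50, log-SD 0.5, raw scale) agrees. Week 12 v baseline:

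| Model or test | Constant | Mild | Stronger |
|---|---|---|---|
| Unstructured | 4.7% | 4.6% | 4.9% |
| Equal correlation | 4.9% | 7.8% | 9.0% |
| Independent visits | 0.3% | 0.8% | 2.1% |
| Planned Wilcoxon | 5.3% | 5.0% | 4.5% |

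For week 2 v baseline, equal correlation gave 2.7% (mild) and 1.9% (stronger).

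**Reading the results.**

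1. The spread of 0.3% to 9% joins independent visits under constant correlation to equal correlation under stronger decline. These are two different true states, and no one study is in both. Across these three models, the mixed-model rates within one pattern run 0.3–4.9%, 0.8–7.8% and 2.1–9.0%. Nor is the spread a bound: over wider assumed correlations, equal correlation ran from 5% to about 14%.
2. The inflation at 8% to 9% is in the contrast for which the SAP also plans a Wilcoxon test, and that test holds its level.
3. At week 2, where the model is the only named test, equal correlation errs on the cautious side.
4. All the distortion comes from a choice that the SAP does not make.

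**The case for a change.** The strongest reply is that the SAP never says unstructured, so the common reading is a courtesy. The Wilcoxon test does nothing for week 2, and at week 4 it appears only within the GDM subgroups. If visits were treated as independent, simulated power at weeks 2 and 4 fell from about 70% to between 19% and 39%, and one added sentence would settle the matter.

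The gap does stand: nothing in either document fills it. The power figures carry less weight. They rest on an assumed effect, and the comparison of equal-correlation with unstructured power changes sign when the effect is applied differently: at constant correlation 74% against 71% in one set-up, 68% against 71% when only the contrasted visit is lowered. Treating visits as independent would also ignore the repetition that the model's own name refers to, so it is a poor guess at what the analysts did.

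A further argument is that the week-12 sample in pregnant women is off therapy, so that only weeks 2 and 4 show on-therapy effects. Protocol 2.6 supports this ("Week 12 (one week after completing IVF hormonal therapy for pregnant group"), but Protocol 2.4 has the same women on therapy up to 12 weeks of pregnancy. Those two statements must be reconciled in their own right. Until they are, the claim that the first aim rests on the mixed model alone is not secure.

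The side points are small. The regression of glucose change had a simulated error rate of 5.4% to 6.9% with no true link. The normality sentence is loosely worded, but the rank tests that follow it are valid whatever the check showed.

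**Conclusion.** The concern does not call for a change. The SAP leaves a modelling detail unstated, and analysts can fill it sensibly: four visits need only 4 variances and 6 covariances, and an unstructured fit held 4.7% to 5.3% in simulation at assumed group sizes of 30 and 60. The harm arises only under a structure that the SAP does not name. Even then, the inflated contrast at week 12 has a planned test with an error rate of 4.5% to 5.3% in the same simulations, and the week-2 contrast under equal correlation is conservative.

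This rests on complete data and assumed correlations. If week-12 dropout depends on the week-4 value, the unstructured model is not exact either: 5.0% to 7.7% in simulation, against 3.2% to 11.8% for equal correlation. The aim is exploratory and the SAP is written in the past tense, so the structure used is already a matter of fact. Stating it with the results is ordinary reporting and corrects no rule in the plan.

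### SAP section 2 clearly specifies change by GDM status only as separate within-group tests; no direct test of whether future-GDM and non-GDM women change differently is secured.

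*SAP*

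**What the plan says.** SAP section 2 (Anthropometrics and Biomarkers of GDM) names three analyses in the pregnant group.

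- A Mann-Whitney U test, "used to compare data at baseline with 12 weeks, for comparison between women who later developed GDM to the non-GDM group".
- Wilcoxon paired tests: "Changes at baseline, 4 and at 12 weeks" "were assessed by non-parametric Wilcoxon test (two related samples) within groups (future GDM or non-future GDM women").
- A regression: "Predictors of GDM were assessed using binary logistic regression, adjusting for the following variables: age and history of PCOS".

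Two sentences in SAP section 1 bear on the point. There the Mann-Whitney test is used to "compare the two groups pregnant vs. non-pregnant, at baseline and at 12 weeks". Changes in glucose, insulin and HOMA-IR "throughout IVF therapy (baseline, 2, 4 and 12 weeks) were determined with the mixed model for repeated measures test".

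The objective served is in Protocol Chapter 1: "To identify possible early predictors of GDM". Protocol section 2.7, Table 1 ("List of Blood Tests at Each Stage of the Study"), shows which markers are measured at which visit.

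**The concern.** Only the Wilcoxon analysis in section 2 is described as an analysis of change, and it runs separately in future-GDM and non-GDM women. It asks whether each group moved, not whether the two moved by different amounts. The second question is a natural one for repeated measures collected with early prediction of GDM in mind.

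If a statement about differential change were made from this plan, the only clearly specified results by GDM status behind it would be two p-values from groups that are probably of unequal size and power. A marker significant in the larger group and not in the smaller one may have changed equally in both. A marker significant in both may still have changed by different amounts. So the comparison can suggest a difference that is not there or hide one that is.

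**Working it through.** **Step 1: does another analysis supply the comparison?**

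- *Mann-Whitney, section 2.* The sentence joins baseline to week 12 by *with*, where section 1 joins them by *and*. The *with* wording allows a comparison of the change. But the sentence does not use the word change, which the SAP uses elsewhere when it means change, and section 1 applies the same test to levels at each visit. Both readings are open, and neither includes week 4, which the Wilcoxon sentence does cover.
- *Mixed model, section 1.* It covers glucose, insulin and HOMA-IR at four visits. No GDM term is stated.
- *Logistic regression, section 2.* Its adjusters are given. Its candidate predictors are not, so change scores are not stated to be among them.
- *Protocol.* It contains no analysis text that fills the gap.

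**Step 2: how misleading could paired p-values be?**

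The documents give no group sizes, SDs, correlations, effects or GDM rate, so there is no planned figure to reproduce. The 0.05 level is from SAP section 1. Everything else is assumed: two-sided tests, normal data, SD 1 at each visit, and correlation rho between visits of 0.4 to 0.8.

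SD of change = sqrt(2(1 − rho)), which is 1.095 at rho 0.4, 0.894 at rho 0.6 and 0.632 at rho 0.8.

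With no change in either group, the chance that exactly one test is significant is 2 × 0.05 × 0.95 = 9.5%. For other settings, 40,000 simulated data sets per setting gave both groups the *same* true change, with a Wilcoxon test in each group and a Mann-Whitney test on change between groups.

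| GDM / non-GDM women | Common true change (SD) | Exactly one group significant |
|---|---|---|
| 15 / 45 | 0 | about 9% |
| 15 / 45 | 0.1 to 0.2 | 14% to 51% |
| 15 / 45 | 0.3 to 0.5 | 21% to 60% |
| 15 / 45 | 0.6 to 0.8 | 1% to 52% |
| 10 / 40 | 0.3 to 0.5 | 41% to 65% |
| 20 / 60 | 0.3 to 0.5 | 9% to 60% |
| 30 / 60 | 0.3 to 0.5 | 2% to 54% |

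The Mann-Whitney test on change was falsely positive in 4.7% to 5.3% of runs throughout. For 15/45, 60% is the peak of the range. The low values arise where both groups are well powered.

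Cross-check: a separate run of 3,000 draws used changes in units of the SD of change. A change of 0.5 SD at rho 0.8 is 0.5 / 0.632 = 0.79 of those units. At 0.8 units and 15/45 that run gave 19%, in line with the 21% above.

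**Step 3: the converse.** With true changes of 1.0 SD (GDM) and 0.4 SD (non-GDM), 15/45 women and rho 0.4 / 0.6 / 0.8, both groups were significant in 58% / 79% / 98% of runs. The direct test detected the difference in 42% / 57% / 86%.

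**Step 4: precision of a direct contrast.** 95% CI half-width = t(58) × sqrt(2(1 − rho)) × sqrt(1/15 + 1/45), with t(58) = 2.002 and sqrt(0.0889) = 0.298:

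- rho 0.4: 2.002 × 1.095 × 0.298 = 0.65 SD
- rho 0.6: 2.002 × 0.894 × 0.298 = 0.53 SD
- rho 0.8: 2.002 × 0.632 × 0.298 = 0.38 SD

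**The case against.** The strongest reply is that the harm depends on an inference the SAP never announces. No objective asks for a comparison of trajectories. The objective on early predictors is answered by the logistic regression, and the Mann-Whitney sentence may already compare change. Much of this stands. A reader might infer that the plan has no between-group GDM test at all, or that it means to judge differential change by setting two p-values side by side. The documents support neither: the Mann-Whitney test does compare the GDM groups, and the SAP states no such rule. Nor are these Wilcoxon tests the SAP's only results on change. Section 1 also has Wilcoxon tests by pregnancy status, a regression of change in glucose and the mixed model. The point is limited to change by GDM status.

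It is also fair that the simulation does not size the problem in this study. Its inputs are all assumed, it tests Mann-Whitney on change and not a GDM-by-visit model, and the converse case is one chosen pair, misleading only if two significant results are read as no difference. The contrasts proposed below also do not adjust for age or PCOS history. They show whether change differs, and prediction stays with the logistic regression. A sentence saying whether change scores enter that regression would help, but would not replace the contrasts.

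The reply does not supply a between-group test of change to week 4, which is missing on either reading, or settle what the Mann-Whitney sentence means.

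**Conclusion.** The point holds as a gap in specification that should be fixed. Change by GDM status is clearly planned only within groups, the one sentence that might compare change is ambiguous, and week 4 is uncovered whichever way it is read. The reading of the text rests on no assumed figures. The size does: about 20% to 60% discordant results with an assumed 15/45 women and an equal change of 0.3 to 0.5 SD, and from about 1% to 65% over all the non-zero changes and group sizes tried, against about 5% for a direct test. It would be wrong to read 60% as this study's error rate. Nothing here shows that the study is invalid or that any reported conclusion rests on the paired p-values.

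**What to change.** In the pregnant group:

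1. For every marker measured at more than two visits, fit a mixed model with GDM status, visit and GDM × visit, transforming skewed markers if needed. Report the difference in change to each visit, including week 4, with a 95% CI. This covers glucose, insulin and HOMA-IR and, if they are analysed in section 2, FSH, LH, oestrogen and progesterone to week 4 as listed in Protocol Table 1. Protocol Appendix 2 lists fewer of these hormones at weeks 2 and 4, so confirm which were taken.
2. For markers taken only at baseline and week 12 (HbA1c, TSH, lipids, adiponectin, LBP, body weight), use Mann-Whitney on the change, with a Hodges-Lehmann shift and 95% CI.
3. State whether the existing Mann-Whitney sentence means levels at each visit or change. If it means change, item 2 needs only clearer wording and the interval estimate.
4. Base any claim of differential change on these contrasts. Keep the Wilcoxon tests as description and the logistic regression as the prediction analysis. The SAP is written in the past tense and the markers are many, so label contrasts that were not prespecified as post hoc and exploratory.

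The cost is a few sentences and GDM terms in a model type the SAP already uses, with no new data. The drawback is imprecision if GDM cases are few: about ±0.38 to ±0.65 SD with the assumed 15/45 women.
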